## ABSTRACT

A large percentage of women suffer low back and pelvic pain both during and after pregnancy. There are several factors to which these complaints are attributed, even affecting their daily lives. It is identified that many of these women do not receive adequate health care, however, different physiotherapeutic interventions are recommended to alleviate these conditions, presenting moderate levels of evidence. Virtual reality is presented as a complementary and promising treatment method to physiotherapy for the improvement of fundamental variables such as perceived pain and pain avoidance. The main objective is to evaluate the efficacy of a combined VR and physiotherapy program of 4 weeks duration compared to a standard physiotherapy intervention in pregnant women with low back pain and pelvic pain for the improvement of pain avoidance, pain intensity, disability and functional level. As a secondary objective we propose to investigate patient satisfaction with the VR intervention. This research will be carried out by means of a multicenter randomized controlled clinical trial in pregnant patients residing in the provinces of Seville and Malaga with a diagnosis of low back pain and pelvic pain during pregnancy. The alternative hypothesis of this research is that the implementation of a Virtual Reality program together with standard physiotherapy in pregnant patients with low back and pelvic pain presents better clinical results obtained with the current standard intervention, which may represent an opportunity to define new policies and interventions for these pathologies and their consequences.

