## Objectives

The main objective of this research is to evaluate the effectiveness of a combined VR and Physiotherapy 4-weeks program compared to a standard physiotherapy intervention in LBP and PP pregnancy woman's to improve pain-related fear avoidance, pain intensity, disability and functional level.

The secondary aim is to investigate patient satisfaction with the VR intervention.

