### Recruitment

In order to generate sufficient data for the development of this research a sample size of (n= 66) patients will be recruited based on previous and concluded RCT for the treatment of LBP or PP (41–43). It was calculated that a sample size of 33 women per cohort could detect a difference in outcomes of 1.0 between the VR intervention and control groups, given a SD of 1.5 and a power of 0.80.

The strategies to achieve an adequate inclusion of participants that reach the target sample size include the multidisciplinary collaboration of the gynecology, rehabilitation and physiotherapy department. The collaborators have been informed about the characteristics of the study in personal interviews and presentation. Recruitment of patients must have a socio-demographic diversity in relation to their social origin, gender, ethnicity and education adapted to the particularities of the reference population.

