## Control Group (CG)

Following clinical practice guidelines, subjects in the control group will receive multidisciplinary rehabilitation programmes with coordinated delivery of supervised exercise therapy, cognitive behavioural therapy (education on pain), as well as therapeutic massage to relieve low back pain during pregnancy.

Typical physiotherapy session:

- Control of daily health
- Analgesic and muscle-relaxing (thermotherapy, tens, therapeutic massage)
- Exercise session:
  - o Initial warm-up: 5–10 min (thoracic, lumbar and pelvic joint mobility exercises adapted to the pregnancy progress).
  - o Strengthening and flexibility exercises (thoracic, lumbar and pelvic joint exercises adapted to the pregnancy progress).
  - o Return to calm: 5 min breath and stretching exercises
  - o Recording of incidents and patient/physiotherapist feedback

Experimental Group (EG). VR intervention:

- o Subjects in the experimental group will receive the same treatment described for the control group
- o Subjects in the experimental group will receive an additional VR intervention.

The immersive virtual reality (VRi) system is composed by a head mounted display (Oculus Quest, Facebook Inc.) and two controllers. Oculus Quest headset is a wireless and portable Android-based device which supports positional tracking with six degrees of freedom (360°). The internal cameras allow to show an external signal with the user view, which helps to monitoring the patient execution. A Wi-Fi connection and a training area of 2x2 meters are needed.

At the end of each session, participants will experience an immersive virtual landscape displayed by Nature Trek VR software (<https://naturetreksvr.com/>). First, participants will be placed in a sit down position and guided for their breathing control during 5 minutes (“meditation Lotus option”). After that, they will be encouraged to freely move around a relaxing virtual environment during 15 minutes taking special attention to soothing sounds of nature. The themed environment will be selected based on the preferences of the participants.

At the beginning of the study, advice is given on general care, in physical activity and issues concerning drug intake. Patients are advised to refrain from any other specific training during the intervention period. Any deviations from the adherence and practice of the VRi are recorded daily, noting any adverse incidents.

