## [Outcomes and Instruments](#)

### [Primary research outcomes](#)

- Pain-related fear avoidance (FACS): The Fear-Avoidance Components Scale (FACS) was developed, which incorporates important components of previous FA-related measures, and includes components of the FA model not previously considered in the earlier-developed questionnaires, within a framework of the most current FA model of Vlaeyen (44,45). The FACS has demonstrated acceptable test/retest reliability ( $r = .90\text{--}.94$ ) and internal consistency (Cronbach  $\alpha=.92$ ) (46).

Pain-related fear avoidance (FA), a common problem for patients with painful medical conditions, involves pain-related catastrophizing cognitions, hypervigilance, and avoidance behaviors, which can ultimately lead to decreased functioning, depression, and disability (47).

- Pain intensity: (Visual Analogue Scale VAS): The VAS has been used in previous studies investigating changes in pain and, specifically, in all the randomized trials of interventions for back pain in pregnancy included in or published since the Cochrane and systematic reviews (42). The visual analog scale (VAS) was used for assessment of pain before and after the intervention. Measurement will be performed with a 10-cm scale marked with 1-cm increments. Pain felt by participants will be recorded. Pain was rated on a scale of 0 a 10, with 10

representing the most excruciating pain. The value indicated on the scale by the participants was used as the score. Previous studies have shown that the reliability of the VAS ( $r=0.76-0.84$ ) is high (46).

- Disability and Physical function: In this paper, we focus on the 2 back-specific measures of function recommended in the “core-set,” the Roland-Morris disability Questionnaire (RMDQ) and the Oswestry Disability Index (ODI). They are the most commonly used measures of function in back pain research (46).

The RMDQ will be used for measurement of the severity of disability in participants who had less severe LBP. There are 24 categories comprised of yes or no questions. Each participant can have a maximum score of 24. Scoring closer to 24 indicates greater functional disability (48,49). Quoted test-retest correlations include 0.91 (same day), 0.88 (1 week), and 0.83 (3 weeks) (48).

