#### [Statistical analysis](#)

This research is a multicentre prospective controlled trial pre/post design. The results of the trial research will be presented as a summary of the outcome measures, together with the estimated effect size and precision. Statistical analysis will be performed according to the intention-to-treat principle. Patient characteristics will be summarized using frequencies and percentages for categorical factors, and using means and standard deviations for continuous measures in order to have as much information as possible available for exploration and analysis. The effect sizes will be calculated using the Cohen's d so that the results can be compared to other studies. The outcome measures will be compared before and after the completion of the 4 weeks program. All statistical analyses will be conducted using SPSS software. Statistical significance was set at  $p < 0.05$ .

[figure not shown]

Figure 1. Study design flow diagram: Enrollment, assessments and intervention stages

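### The only comparison named in the statistical analysis section is pre versus post, with no between-arm contrast, so it does not secure an answer to the randomised question

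*Protocol*

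**What the plan says.** The Statistical analysis section describes a "multicentre prospective controlled trial pre/post design" analysed by intention to treat. Its one sentence about a comparison is "The outcome measures will be compared before and after the completion of the 4 weeks program". Effect sizes are to be reported, with this purpose: "The effect sizes will be calculated using the Cohen's d so that the results can be compared to other studies". Whether Cohen's d is taken between arms or within an arm is not said.

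Elsewhere the Protocol asks a between-arm question:

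- Abstract: the hypothesis is that VR with physiotherapy "presents better clinical results obtained with the current standard intervention".
- Objectives: the aim is to "evaluate the effectiveness of a combined VR and Physiotherapy 4-weeks program compared to a standard physiotherapy intervention".
- Recruitment: the trial is sized to "detect a difference in outcomes of 1.0 between the VR intervention and control groups".

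On treatment, the Intervention text says: "Subjects in the experimental group will receive the same treatment described for the control group". VR is added on top. Table 1 admits only women with VAS pain above 4/10.

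**The concern.** The comparison stated for analysis is not the one on which the trial was justified and sized. An analyst working from the Statistical analysis section alone could run a paired test in each arm and comply with it.

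In this trial that would mislead. Both arms receive an active programme, and selection on a pain threshold brings regression to the mean in VAS, so change from baseline can be expected without any contribution from VR. A significant change in the VR arm, or one significant there and not in the control arm, is therefore not evidence for VR. The Results section would count beneficial effects as support for VR without saying on which comparison they are judged, so the analysis section has to settle it.

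**Working it through.** **Inputs from the Protocol.** 33 women per arm, difference 1.0, SD 1.5, power 0.80 (Recruitment; the outcome is not named); significance level 0.05 (Statistical analysis; two-sided assumed).

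**Assumed.** SD of change 1.5 (1.2 and 2.0 also tried) and an improvement common to both arms of 0.5, 0.75 or 1.0 points. The Protocol gives neither.

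**Step 1: the plan's own figure.** For a two-sample t test, λ = 1.0 / (1.5 × √(2/33)) = 2.708 on 64 df, which gives power 0.760. Power 0.80 needs 37 per arm two-sided, or 29 one-sided, so 33 does not reproduce. That is a separate matter; nothing below depends on it.

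**Step 2: pre/post test within one arm.** λ = (improvement / SD of change) × √33, and w = P(|T| > 2.037) on 32 df. The arms are independent. With no VR effect, 'VR arm significant, control not' has probability w(1 − w). With a true VR effect of 1.0, the VR arm's own test has power v ≈ 1.0 and the pattern has probability v(1 − w).

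| Common improvement | λ | w | VR only, no effect | VR only, effect 1.0 | Both significant, no effect | Both significant, effect 1.0 |
|---|---|---|---|---|---|---|
| 0.5 | 1.915 | 0.459 | 0.248 | 0.541 | 0.211 | 0.459 |
| 0.75 | 2.872 | 0.795 | 0.163 | 0.205 | 0.633 | 0.795 |
| 1.0 | 3.830 | 0.960 | 0.038 | 0.040 | 0.922 | 0.960 |

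With no effect, 'VR only' is 0.230, 0.060 and 0.004 at an SD of change of 1.2, and 0.204, 0.247 and 0.163 at 2.0.

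**Step 3: between-arm test of change.** With an SD of change of 1.5, it rejects in 5% of trials under no effect and in 76% under an effect of 1.0, whatever the common improvement. At a common improvement of 1.0, the pre/post patterns are almost the same with and without a VR effect (4% and 4%; 92% and 96%). At 0.5 they separate partly (25% and 54%; 21% and 46%).

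**Step 4: regression to the mean alone (VAS).** Assume a population mean of 4.5, SD 1.5, pre/post correlation 0.5, entry above 4, and no treatment effect in either arm. Mean T0 among entrants is 5.40, and expected T1 is 4.5 + 0.5 × (5.40 − 4.5) = 4.95, a fall of 0.45. The SD of change is 1.39. Each arm's paired test is then significant with probability 0.436, and 'VR only' has probability 0.436 × 0.564 = 0.246. A simulation of 20,000 trials gave 0.429 and 0.241. For population means of 4.0 and 6.0 the per-arm figure is 0.679 and 0.082.

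**Step 5: T0 adjustment (secondary).** The residual SD is 1.5 × √(1 − r²), on 63 df. Power for a difference of 1.0 is 0.798, 0.829 and 0.868 for r = 0.3, 0.4 and 0.5, against 0.760 unadjusted.

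**The case against.** The strongest reply is that the sentence only names the measurement times. The VAS text uses the same phrase in that sense: the scale "was used for assessment of pain before and after the intervention". The hypothesis, objective and sample size are all comparative, the section calls the trial controlled, and intention to treat has its usual meaning only for randomised arms. Nothing prescribes a paired test. This stands: the text permits a within-arm analysis but does not require one, and the between-arm intent can be recovered from other sections. It does not remove the gap, because the section that fixes the analysis never states that intent.

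A second reply is that tests, models and covariates belong in an SAP. That holds for the details of T0 adjustment. It does not hold for which comparison answers the objective, where the Protocol is not silent but states one that does not match.

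A third is that the figures are all assumed. The Background says this pain tends to increase as pregnancy advances, which works against a fall from baseline. In the Step 4 scenario, an assumed worsening of 0.25 points lowers the per-arm figure from 44% to about 13%, and 0.45 points returns it to 5%. Step 4 also concerns VAS alone, and the improvements and SDs used are not calibrated to FACS, RMDQ or ODI. These limits are fair. They weaken the regression-to-the-mean illustration but not the main point, which needs only that change can occur in both arms for reasons other than VR.

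**Conclusion.** The concern holds and should be fixed. The one comparison that the analysis section states names no arm, and if followed as a within-arm test it cannot show what VR adds to physiotherapy. This is a mismatch within the Protocol, not proof that the wrong analysis will be run.

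The size depends on the common improvement, which the Protocol does not give. Across the assumed range, with no VR effect, the VR arm's own test is significant in about half to nearly all trials, and the 'VR only' pattern arises in up to a quarter. The between-arm test keeps its 5% error rate in every case. That contrast, rather than any single percentage, is the reason to change the text.

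**What to change.** Replace the comparison sentence in the Statistical analysis section with wording such as:

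> The primary analysis compares the randomised arms at T1, adjusted for the T0 value of the same scale (ANCOVA). The adjusted between-arm difference with its 95% confidence interval, and Cohen's d for that difference, will be reported. Within-arm changes are descriptive only.

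Naming the between-arm contrast is the essential part. T0 adjustment is recommended for precision, and its details may be left to the SAP.

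The cost is one sentence. T0 and T1 scores are already collected for all four primary scales, SPSS fits the model, and the covariate uses one degree of freedom. No extra patients or visits are needed.

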## Results:

Enrollment began in September 2022. First study results will be reported at the end of 2022. The results of this study will determine if a larger-scale intervention is feasible. Further, this pilot study will be the first to examine the effect of the VR intervention on LBP and PP in pregnancy woman. If the results confirm beneficial

effects in the outcomes, this study will add more evidence in support of the use of VR program as an effective tool in pregnancy with LBP and PP rehabilitation programs.

#### Discussion:

Evidence from single studies suggests that some therapy modalities or a multi-modal intervention (manual therapy, exercise and education) improves pelvic pain and pregnancy related outcomes. However, the current scientific evidence leaves many issues unresolved like type and intensity of exercise and physiotherapy intervention effectiveness for different outcomes. Since evidence showing that one form of exercise is better than another is not available, guidelines recommend exercise programmes that take individual needs, preferences, and capabilities into account in deciding about the type of exercise. This lack of standardized exercise programmes may lead to significant intervention biases in the different studies and consequently the low or moderate level of evidence.

Due to the high prevalence, the recurrence, the interference on daily activities, work capacity and sick leaves, and the increased psychological stress (1–4), low back pain is undoubtedly the key clinical sign to address in this population.

The VRi used in this case may alleviate pain by distracting the patient's attention from pain. The alleviation of pain is thought to be the psychological effect of immersion in the virtual space created by the VR technology (51). Another mechanism by which the VR program can reduce pain would be the creation of a relaxing atmosphere. Perception of pain is influenced by the patient's affect (52). Therefore, the positive effect induced by the psychological effects of the VR relaxation program could suppress pain perception (53).

This research should provide knowledge about the possibility of implementing VR programs in clinical environment, identifying new intervention opportunities in this group of patients.

Technical problems like device failures and technological difficulties may arise in connection with the use of VR technology. However, staff members are available to provide technical support. As possible adverse events we consider

the lack of improvement and positive evolution of the patient. We also consider as an adverse event the performance of exercise with excessive workload. Patients will be informed of the importance of warning the health professional of any incident or setback in their recovery and their right to withdraw from participation in the research at any time.

Future lines of research would involve the development of clinical trials with a large sample size and the opportunity to develop a multicenter randomized clinical trial with standardize physiotherapy and exercise programmes

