### Intervention

Participants will be assigned randomly to the intervention or control groups using a random number table. Both groups will receive 3 sessions per week during the 4 weeks of intervention.

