#### Data collection, monitoring, and management

Once participants have been informed and agree to participate in the study, data will be collected for statistical analysis. This data collection will take place in the period September-December 2022. Initial assessment (Pre) and final 4-week assessment (Post) will be carried out by the research team including, rehabilitation and physiotherapy department. The data will be aggregated to research database created for this purpose and managed by the principal's researches using exportable data tables for statistical analysis.

The research is designed in 4 stages as presented at Figure 1 study design flow diagram:

Stage 1 includes 2 different processes: firstly the identification of candidates, the provision of prior information and the signing of informed consent if subjects agree to participate. Secondly, the assessments by the physiotherapy department. The initial assessment includes a self-made clinical interview for anamnesis with self-administered questionnaires, which will be completed including FACS, RMDQ, ODI and VAS (T0-Pre). This stage ends with the referral to the physiotherapy intervention team.

Stage 2 includes: Design of a personalised physiotherapy programme (CG and EG) according with Physiotherapy department plus VRi intervention in the (EG).

Stage 3 includes: 4 weeks physiotherapy intervention plus VRi program with the supervision of the physiotherapy department. Initials 1 to 1 session is offered with technology management and patient education. Daily follow up sessions include the progression and adverse events records. Physiotherapy team will update programmes according to participant's feedback.

Stage 4 includes: Final assessments and evaluation (T1-Post). At this stage Physiotherapy team and principals researches compile the results of outcomes after 4 weeks including FACS, RMDQ, ODI, VAS and USEQ. Satisfaction questionnaire will be added to research data's for statistical analysis.

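### The protocol classes lack of improvement as a possible adverse event, so the adverse-event record can mix non-response with harms

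*Protocol*

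**What the plan says.** The Discussion introduces a short list of possible adverse events. The first item is "the lack of improvement and positive evolution of the patient". The sentence runs across a page break, but its sense is clear, and the next sentence adds exercising at too high a workload as a further adverse event. The paragraph then widens what should be reported: "Patients will be informed of the importance of warning the health professional of any incident or setback in their recovery".

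Three other places bear on this:

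- **Objectives.** The combined programme is meant to "improve pain-related fear avoidance, pain intensity, disability and functional level".
- **Data collection, monitoring, and management.** On timing: "Initial assessment (Pre) and final 4-week assessment (Post) will be carried out by the research team". At Stage 4 the team will "compile the results of outcomes after 4 weeks including FACS, RMDQ, ODI, VAS and USEQ". At Stage 3, during treatment: "Daily follow up sessions include the progression and adverse events records".
- **Control Group and Experimental Group.** The typical physiotherapy session, which both arms receive, ends with "Recording of incidents and patient/physiotherapist feedback". The experimental-group text adds a daily record of departures from VR practice, in which adverse incidents are noted.

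No other part of the protocol says what an adverse event is.

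**The concern.** An adverse-event record should show what happened to participants that was unwanted, whether or not the treatment worked. Failure to improve is the opposite of the trial's efficacy aim. Once it is classed as an adverse event, the record holds two different things, and a reader of a summary cannot tell them apart unless each entry is traced back to its reason.

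The harms record matters here. The participants are pregnant women using an immersive headset. The protocol's Background says there is no evidence on the effectiveness of VR for this condition in pregnancy, and its Results section says the study will inform whether a larger intervention is feasible. An adverse-event table containing non-responders would be a poor basis for that decision.

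**Working it through.** The point rests on no sample-size, power or event figure, and the protocol gives no adverse-event figure to reproduce. The check is a comparison of the texts.

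1. **Is lack of improvement really classed as an adverse event?** Yes. The sentence introduces possible adverse events and names it first. The following sentence opens by saying that a second thing is *also* considered one, which confirms how the first is meant.

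2. **Is it the same thing as the efficacy objective?** Yes. The Objectives section defines success as improvement in fear avoidance, pain intensity, disability and function. FACS, VAS, RMDQ and ODI measure these at T0 and T1. A woman with no improvement on them has not met the aim, and nothing further need have happened to her.

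3. **Does the protocol already have another place for it?** Yes, two. The efficacy scales capture it at T1. During treatment, Stage 3 names progression and adverse events as separate items at the daily sessions. The Discussion merges what Stage 3 keeps apart.

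4. **Does any other text correct the Discussion?** No. The intervention and data-collection sections speak of *incidents*, *adverse incidents* and *adverse events* without defining any of them or saying that non-response is kept out.

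5. **What would a summary by arm contain?** For each arm, let H be the recorded harms and N the entries made only for lack of improvement. With E for the experimental and C for the control arm, the recorded totals are

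   A_E = H_E + N_E and A_C = H_C + N_C,

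   so A_E − A_C = (H_E − H_C) + (N_E − N_C).

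   The second bracket is an efficacy contrast. If N_E = N_C it vanishes from the difference, but both totals are still raised by entries that are not harms. If N_E and N_C differ, the difference carries efficacy into a safety figure. The protocol gives no value for N and no criterion for judging lack of improvement at a session, so neither bracket can be sized.

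**The case against.** The strongest reply is that little follows from the wording. It stands in the Discussion, speaks only of *possible* adverse events and gives no criterion for applying it. Adverse events are not among the listed outcomes, and the Statistical analysis section plans no count or comparison of them. All of this is correct, and it keeps the point minor. It does not remove it, because this is the only text that gives the term any content for whoever completes the Stage 3 record.

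Several stronger readings are tempting, and the documents do not support them:

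- **That the adverse-event comparison would favour VR.** A reader might infer this from the trial's hypothesis that adding VR gives the better result, which would put more non-response entries in the control arm. But the experimental-group text provides an additional daily note of adverse incidents tied to VR practice, which only that arm can generate and which could raise its count. With two opposing influences, neither of them sized, the net direction cannot be stated.
- **That the entry would duplicate the efficacy result at T1.** The adverse-event record belongs to the Stage 3 sessions. The Stage 4 text schedules the scales and mentions no adverse-event record.
- **That real harms are shut out.** The Discussion list is not exhaustive. Women are asked to report incidents and setbacks generally, and the session common to both arms records incidents. The fault is in what is let in.
- **That the number of scheduled sessions measures the problem.** It counts opportunities to make an entry and says nothing about how many such entries there would be.
- **That excessive workload should be moved out as well.** It is not an efficacy failure, and nothing in the documents argues for classing it differently.

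**Conclusion.** The point holds in a limited form. The protocol states a misclassification: it calls non-response a possible adverse event, although its own Objectives and data-collection sections treat the same thing as efficacy and progression. If the wording is followed, the adverse-event record can mix the two, and any summary made from it would partly reflect efficacy.

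Severity is minor. The size and net direction are unknown, no bias is shown, and the efficacy analysis is untouched. The conclusion assumes that staff would apply the Discussion wording when completing the daily record, and that some adverse-event summary will eventually be reported. The protocol does not plan one; a statistical analysis plan, if there is one, was not available to check.

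**What to change.** Delete lack of improvement from the adverse-event wording in the Discussion. Report it only through FACS, VAS, RMDQ and ODI and through the progression record at the daily sessions. Leave worsening and setbacks reportable as they are now, and leave the classing of excessive workload unchanged.

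Use one adverse-event term with one meaning, applied in both arms, in the Control Group and Experimental Group text, in Stage 3 of the data-collection section and in the Discussion.

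The cost is a small wording change, since the daily record already exists and no new data are needed. The downside is that the protocol's Results section says enrolment began in September 2022. Any entry already made as an adverse event solely for lack of improvement would need to be identified before a safety summary is prepared. The protocol does not show whether any such entry exists.
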